# 8 BENEFIT-RISK EVALUATION

# 8.1 Benefit of BT524

Fibrinogen plays a critical role in achieving and maintaining hemostasis in patients undergoing major surgeries and the observation that patients with higher fibrinogen levels experience fewer bleeding complications than those with low levels highlights the importance of fibrinogen in the maintenance of hemostasis. Consequently, fibrinogen replacement therapy targeting a high-normal level of plasma fibrinogen and fibrin-based clot formation may be an important first step in restoring hemostasis during major bleeding.

Major spinal and abdominal surgeries represent elective surgeries often associated with significant intra- and post-operative blood loss resulting in decreased fibrinogen levels. An accurate and rapid determination of (functional) fibrinogen level is important during hemorrhage to establish a timely hemostatic intervention. Individualized dosing of fibrinogen concentrate using a target ROTEM/FIBTEM value integrates rapid diagnostic testing with appropriate therapeutic dosing of fibrinogen concentrate according to patients' needs.

The principal benefit for the participating subjects randomized to the BT524 treatment arm will be to receive the required individualized fibrinogen replacement therapy in a goaldirected treatment algorithm as a timely hemostatic intervention if significant bleeding is accompanied by acquired hypofibrinogenaemia. Moreover, fibrinogen concentrate seems to have certain advantages over the standard replacement therapy with FFP/cryoprecipitate, such as precisely determined, high amount of purified fibrinogen dissolved in a small volume, low risk of pathogen transmission and instant administration without need for thawing or testing AB0 blood group compatibility.

# 8.2 Foreseeable Risk and Discomfort Related to BT524

At that point of time the pre-clinical and clinical study data are still considered too scarce to finally define risks as "identified" in the context of BT524. Therefore at present all signals as derived from class-labelling, currently remain to be regarded as potential risks. Please also refer to section 6.11 Warnings and Precautions.

# 8.3 Other Sources of Possible Risk and Discomfort

Please refer to section 6.11 Warnings and Precautions.

# 8.4 Summary of Possible Risk and Discomfort

Human fibrinogen concentrate is a well-known substance, established for decades in the treatment of congenital fibrinogen deficiency as well as of various indications of acquired fibrinogen deficiency. Fibrinogen concentrates have shown to be safe and well-tolerated (Fenger-Eriksen et al., 2009; Henselmans et al., 1999).

A Guideline for Core SmPC for Human Fibrinogen Products (EU Core SmPC) is in place which also describes the well established benefit-risk profile of the authorized fibrinogen concentrates (EMA (Committee for Medicinal Products for Human Use), 2015).

It provides the following AEs as undesirable effects considered established for all authorized and marketed human fibrinogen concentrate formulations: In the MedDRA SOC "Immune system disorders": Allergic or anaphylactic-type reactions; in the MedDRA SOC "Vascular disorders": Thromboembolic episodes (including myocardial infarction

and pulmonary embolism); and in the MedDRA SOC "General disorders and administration site conditions": Increase in body temperature.

Currently, there is no data with human fibrinogen products in regard to inhibitor formation.

With regard to transmissible agents refer to section 6.11 Warnings and Precautions.

The safety profile of BT524 is anticipated to be in line with the marketed fibrinogen concentrates and the content of the EU Core SmPC [Guideline on Core SmPC for Human Fibrinogen Products (EMA/CHMP/BPWP/691754/2013 Rev 1)].

The safety and tolerability and the benefit-risk profile of BT524 (fibrinogen concentrate from human plasma) is considered favorable.

# 9 ASSESSMENT OF OBJECTIVES / CRITERIA FOR EVALUATION

# 9.1 Efficacy

#### 9.1.1 Specification of Efficacy Parameters

#### 9.1.1.1 Primary Efficacy Parameter

The primary efficacy parameter is determined from the intra-operative blood loss after the decision to treat the subject with IMP until the end of the surgery as measured by the amount of blood from the blood suction unit and the amount of blood from swabs, surgical cloths and compresses.

# 9.1.1.2 Secondary Efficacy Parameter

Secondary efficacy will be determined using the following parameters:

- Proportion (%) of subjects with successful correction of fibrinogen level (FIBTEM A10) 15 minutes after start of first IMP administration
- Time to first successful correction of fibrinogen level (15 minutes or 90 minutes after start of first IMP administration, end of surgery, not within surgery)
- Total amount (volume in mL and number of units) of transfusion products (allogenic blood products) or autologous blood transfusion infused after start of first IMP administration until end of surgery
- Amount (volume in mL and number of units) of RBCs (allogenic and autologous) infused after start of first IMP administration until end of surgery
- Post-operative blood loss in the first 24 hours
- Proportion (%) of subjects with rebleeds after the end of surgery until Day 8
- Hospital length of stay after surgery
- In-hospital mortality

9.1.2 Methods for Assessing and Recording Efficacy Parameters

#### 9.1.2.1 Methods for Assessing Primary Efficacy Parameter

#### Amount of Blood Loss

The blood loss will be quantified by measuring the continuous bleeding mass with a **blood suction unit** and by calculation of the amount of blood from **swabs**, **surgical cloths and compresses** (see section 3).

The **blood suction unit** will be used to remove fluid and blood from the area being operated. Allowance must be made also for the presence of **mucinous ascites**. After opening and inspection of the abdomen the inside of the abdominal cavity will be washed out with a certain amount of **irrigation solution** (physiological saline solution) to remove mucinous ascites.

Prior to the start of surgery the weight of **dry swabs**, **surgical cloths and compresses** will be recorded (weighing of swabs is required if weight is not specified on the packaging). In case a **manual compression** is necessary during surgery, dry swabs, surgical cloths and compresses will be applied to the surgical field, afterwards removed and wrung out until almost dry. By wringing out surgical cloths, the blood can be caught in a kidney dish and finally collected in the suction container. Subsequently, all cloths and compresses will be weighed (before they dry out) and the weight will be recorded.

# For the primary endpoint the amount of blood loss will be measured from the time of decision to treat the subject with IMP until the end of the surgery:

Immediately after the prediction of an intra-operative clinically relevant bleeding of more than 2 L, and the assessment that hemostatic treatment will be required during surgery (high risk for the need of fibrinogen supplementation, either with cryoprecipitate or BT524 during surgery), the person responsible for randomization will be informed about the decision to treat the subject with IMP. At the same time, the **suction container will be emptied and the blood measurement for the primary endpoint is initiated** with collection of blood in the empty blood suction unit.

In addition, in case a manual compression is necessary after decision to treat the subject with IMP, **new** swabs, surgical cloths and compresses will be applied to the surgical field.

At the end of the surgery, all **swabs**, **surgical cloths and compresses** will be removed from the surgical field, wrung out (blood will be collected in the suction container) until almost dry and weighed. The weight will be recorded. The end of surgery is defined as time of last suture.

The **fluid volume** collected in the blood suction container will be measured and documented.

The amount of **irrigation solution** suctioned into the container through irrigation of the wound must be calculated. This can be done by knowing the capacity of the irrigation syringe in use and keeping track of the number of times it is used. The calculated amount of irrigation solution must also be recorded.

The amount of irrigation solution will be subtracted **from the entire fluid volume in the suction container** to determine the actual amount of blood collected in the suction container.

PPD

In a final step the **total blood loss will be calculated**. The calculation of blood loss based on the volume of blood removed from the surgical field by the blood suction unit and that absorbed by swabs, surgical cloths and compresses.

### 9.1.2.2 Methods for Assessing Secondary Efficacy Parameter

#### Correction of Fibrinogen Level via FIBTEM A10 (mm)

The correction of the fibrinogen level will be measured via thromboelastometry (ROTEM/FIBTEM A10). ROTEM is an established viscoelastic method for hemostasis testing in whole blood and ROTEM/FIBTEM that measures the fibrin or fibrinogen contribution to clot strength, can be used to determine the most appropriate therapeutic dose of fibrinogen concentrate (Levy et al., 2014).

Whole blood viscoelastic tests such as the fibrin-based thromboelastometry (ROTEM) test FIBTEM will be used in the intra-operative setting to quickly identify deficits in fibrin quality, and to guide hemostatic therapy. In contrast to conventional laboratory tests (measurement of fibrinogen concentration via Clauss assay), ROTEM/FIBTEM can measure early variables describing the clot firmness, such as clot amplitude obtained after 5 minutes (A5) or 10 minutes (A10), and provide a forecast on the expected MCF value at an earlier stage already. These early variables allow for a more rapid decision about therapeutic interventions.

The fibrinogen activity will be measured by FIBTEM A10, MCF and Clauss assay at screening, prior surgery (baseline), pre-dose, 15 and 90 minutes after the start of first IMP administration, at the end of the surgery and one day after surgery.

For the evaluation of the secondary efficacy endpoint successful correction of the fibrinogen level is defined as restoring fibrinogen FIBTEM A10 baseline levels measured by ROTEM 15 minutes after start of first IMP administration.

Accordingly, the time to first successful correction of fibrinogen level is defined as the time point (15 minutes or 90 minutes after start of first IMP administration, end of surgery, not within surgery) the fibrinogen FIBTEM A10 baseline levels measured by rotational thromboelastometry are restored the first time.

However, correction of fibrinogen will also be analysed based on results obtained from MCF and Clauss assay to perform sensitivity analyses.

#### Clauss Assay

The most widely used technique for determination of fibrinogen concentration is the Clauss (FIBClauss) assay (Clauss, 1957). In this method, dilutions of a plasma standard of known fibrinogen concentration are clotted by addition of a high concentration of thrombin, and a standard curve is prepared. Because the clotting time is inversely proportional to the fibrinogen concentration, the clotting time of diluted patient plasma is used to read the fibrinogen concentration from the standard curve. This method is reliable, accurate, and precise, and easily adapted to automated coagulation analyzers.

Maximum Clot Firmness (MCF, mm)

MCF addresses the clot integrity and will be measured by ROTEM® (ROTEM delta or ROTEM sigma).

MCF will be determined locally from whole blood or at the central laboratory by means of the Fib-tem S assay (tissue factor activation and platelet inhibition), a ready-to-use ROTEM system reagent (PPD , Mar 2011) for the ROTEM delta/sigma which allows the assessment of the fibrinogen level and the quality of the fibrin polymerization in citrated blood by inhibiting the platelets. For ROTEM sigma the FIBTEM C system reagent will be used accordingly.

Fibtem measures the viscoelastic properties of the clot and provides information on the speed of coagulation initiation, kinetics of clot growth (MCF, mm), clot strength, and breakdown(Lang et al., 2009). **Figure 4** shows an example of the ROTEM readout of citrated normal blood.

# Figure 4: ROTEM Readout of Citrated Normal Blood

The ROTEM® analyses: FibTEM® test (fibrin clot obtained by platelet inhibition with cytochalasin D). The clotting time (CT (seconds)) represents the time from the start of the test until a clot firmness of 2 mm is detected; maximum clot firmness (MCF (mm)) represents the total amplitude of the clot (Schöchl et al., 2010).

In the ROTEM read out of Fib-tem S test expected reference (normal range) values for the amplitude of MCF are 9-25 mm for fibrinogen levels (Fib-tem S 2011).

# Consumption of Transfusion Products

The **amount of transfusion products** (allogenic blood products or autologous blood transfusion) given after start of first IMP administration until end of surgery to counteract hemodynamic instability will be documented (volume in mL and number of units if applicable) and evaluated.

The **amount of RBCs** (allogenic and autologous) required intra-operatively after start of first IMP administration until end of surgery will be documented (volume in mL and number of units if applicable) and evaluated.

PPD

#### Postoperative Blood Loss (Drainage Volume)

The plasma drainage tube and disposable drainage bag will be emptied 24 hours after the end of the surgery. The end of surgery is defined as time of last suture. The drainage volume will be measured and postoperative blood loss will be recorded.

#### Rebleeds

Any bleed judged by the surgeon and/or the anaesthesiologist as requiring hemostatic treatment (including reoperation) after the end of the surgery until follow-up Day 8 will be recorded. The end of surgery is defined as time of last suture.

#### Hospital Length of Stay after Surgery

The day of the surgery and the day of the discharge from hospital will be recorded.

The hospital length of stay after surgery is used to compare the number of days patients stayed in the hospital after surgery. The hospital length of stay after surgery is calculated by the following formula:

Length of stay after surgery = date of discharge - date of surgery

#### In-hospital Mortality

In-hospital mortality is defined as death occurring during the hospital stay. A death during hospitalization will be recorded as an SAE.

#### 9.1.3 Specification of Efficacy Endpoints

# 9.1.3.1 Specification of Primary Efficacy Endpoint

Intra-operative blood loss as measured by amount of blood from the blood suction unit and amount of blood from swabs, surgical cloths and compresses after the decision to treat the subject with IMP until end of surgery. The end of surgery is defined as time of last suture.

#### 9.1.3.2 Specification of Secondary Efficacy Endpoints

• Proportion (%) of subjects with successful correction of fibrinogen level 15 minutes after start of first IMP administration.

Successful correction of fibrinogen level in a subject is defined as restoring fibrinogen FIBTEM A10 baseline level to at least 95% measured by ROTEM 15 minutes after start of first IMP administration. A correction of at least 95% is considered successful, as measurement methods has a coefficient of variation of about 5% (Solomon et al., 2015).

- Time to first successful correction of fibrinogen level (15 minutes or 90 minutes after start of first IMP administration, end of surgery, not within surgery).
- Total amount of transfusion products (allogenic blood products) or autologous blood transfusion infused after start of first IMP administration until end of surgery. The end of surgery is defined as time of last suture.

- Amount of RBCs (allogenic and autologous) infused after start of first IMP administration until end of surgery. The end of surgery is defined as time of last suture.
- Post-operative blood loss in the first 24 hours.
- Proportion (%) of subjects with rebleeds. Rebleeds are defined as any bleed requiring hemostatic treatment (including reoperation) after the end of surgery until Day 8.
- Hospital length of stay after surgery, defined as the date of discharge minus the date of surgery.
- In-hospital mortality.

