8.2 Baseline

If not stated otherwise, the last non-missing valid observation prior to surgery will serve as the baseline measurement.

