8.12 Correction of Fibrinogen Level

The fibrinogen level is assessed by FIBTEM A10 test, MCF and Clauss assay at the following visits: screening, prior surgery (baseline), Surgery Day 1 (Prior 1st dose), Surgery Day 1 (Predose)*, Surgery Day 1 (15 minutes after start of first IMP administration), Surgery Day 1 (90 minutes after start of first IMP administration), Surgery Day 1 (end of surgery), and Day 2, Follow-up Visit. (* only applicable in case of repeated intra-operative IMP administration).

Rate of fibrinogen restoring = fibrinogen level at a post-baseline visit / fibrinogen level at baseline*100

If the rate of fibrinogen restoring is \geq 95%, then the fibrinogen level is considered to be successfully corrected at that post-baseline visit for the subject.

The above rate will be calculated for the following visits: Surgery Day 1 (15 minutes after start of first IMP administration), Surgery Day 1 (90 minutes after start of first IMP administration), Surgery Day 1 (End of surgery), and Day 2, Follow-up.

The time to first successful correction of fibrinogen level is classified into the following categories: "Within 15 minutes after IMP start", "Greater than 15 and less than or equal to 90 minutes after IMP start", "Greater than 90 minutes after IMP start" and "Unsuccessful correction".

At every visit, the time point relative to the start time of IMP is calculated in minutes as Collection Time of sample minus Start Time of IMP. Any corrections <15 minutes after IMP start are not considered for classification.

The earliest time point, when the rate is \ge 95%, is the time to first successful correction of fibrinogen level and will be used to categorize the subjects into the respective categories.

Subjects with time to first successful fibrinogen correction on Follow-up Visit Day 2 will be assigned to the category "Greater than 90 minutes after IMP start". If the rate of fibrinogen restoring is < 95% at all the time points, correction of fibrinogen level is reported as "Unsuccessful correction".

A sensitivity analysis adds a time window of ±3 minutes to the category "Within 15 minutes after IMP start", so that time points ≥12 and ≤18 minutes fall into this category. To the category "Greater than 15 and less

than or equal to 90 minutes after IMP start" a time window of +3 minutes is added, so that time points between >18 and ≤93 minutes fall into this category. Corrections >93 minutes are categorized as "Greater than 90 minutes after IMP start".

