12.5.2 Multiplicity

The primary variable is only tested for superiority when the non-inferiority is demonstrated by the primary analysis, which will not lead to inflation of the Type-I error.

The statistical analyses on secondary variables are of exploratory nature. No adjustment for multiplicity is needed.

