12.5.3.1 Correction of Fibrinogen Level

The proportion (%) of subjects with a successful correction of fibrinogen level (by FIBTEM A10) 15 minutes after start of first IMP administration will be compared between the treatment arms using a Cochran-Mantel-Haenszel (CMH) approach stratified by predictive blood loss (> 1,000 mL to \leq 2,000 mL and > 2,000 mL). The number and percentage of subjects with a successful correction of fibrinogen level 15 minutes after start of first IMP administration will be presented for both treatment arms with corresponding 95% confidence intervals. The estimated treatment effect (i.e., the difference in response rate between the treatment arms, BT524 – FFP/cryoprecipitate), corresponding 95% confidence interval, and 2-sided p-value for the difference will be presented.

The time to first successful correction of fibrinogen level (by FIBTEM A10) is assigned to the following categories: "Within 15 minutes after IMP start", "Greater than 15 and less than or equal to 90 minutes after IMP start", "Greater than 90 minutes after IMP start" and "Unsuccessful correction". The 4 categories will be compared between the two treatment arms using a Chi-square test.

In an additional analysis the time to first successful correction of fibrinogen level (by FIBTEM A10) is classified relative to the end of surgery into "Until end of surgery", "Not within surgery" or "Unsuccessful correction". The 3 categories will be compared between the two treatment arms using a Chi-square test.

For the above Chi-square tests, the number and percentage of subjects in each category will be presented for each treatment arm, together with an overall p-value for the difference between the two treatment arms.

The absolute values and change from baseline in fibrinogen levels by FIBTEM A10, together with the rate of fibrinogen restoring will be summarized with descriptive statistics over time by treatment arm. The absolute values at screening and change from screening at baseline will also be summarized for fibrinogen levels by FIBTEM A10.

In addition, the test results of MCF and Clauss assay will be summarized in the same way. The results of these three assays will be listed for the All Subjects Enrolled Set.

Mean with SD, median with interquartile ranges will be presented graphically over time for both treatment arms for FIBTEM A10, MCF and Clauss assay.

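### The 95% cut for fibrinogen correction is justified by the error of one reading but applied to a ratio of two; the ratio itself should also be compared between arms

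*Protocol*

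**What the plan says.** Protocol 9.1.3.2 defines success as a FIBTEM A10 of at least 95% of baseline 15 minutes after the first IMP administration starts. Its only justification is "A correction of at least 95% is considered successful, as measurement methods has a coefficient of variation of about 5" per cent, with a literature citation. Protocol 9.1.2.2 words the same definition without any tolerance: "successful correction of the fibrinogen level is defined as restoring fibrinogen FIBTEM A10 baseline levels measured by ROTEM 15 minutes after start".

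SAP 8.12 turns the definition into a calculation: "Rate of fibrinogen restoring = fibrinogen level at a post-baseline visit / fibrinogen level at baseline*100". A value of 95% or more is a success. The denominator is one measurement, because SAP 8.2 states that "the last non-missing valid observation prior to surgery will serve as the baseline measurement".

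In SAP 12.5.3.1 the proportion of successes "will be compared between the treatment arms using a Cochran-Mantel-Haenszel (CMH) approach stratified by predictive blood loss". The same cut feeds the time-to-correction categories, which are compared by chi-square tests. The continuous quantity is treated differently: absolute values and changes, "together with the rate of fibrinogen restoring will be summarized with descriptive statistics over time by treatment arm". No between-arm estimate or test is planned for it.

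SAP 8.12 repeats the analysis with MCF and Clauss results. SAP 12.5.2 gives the status of all this: "The statistical analyses on secondary variables are of exploratory nature".

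**The concern.** The tolerance and the variable do not match. A 5% allowance corresponds to one CV of a single reading. The variable compared with 95% has error in the numerator and in the denominator, so its spread is wider than the rationale implies, and more subjects near the cut land on the wrong side of it in both directions.

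The cut defines the first two secondary efficacy endpoints. The planned sensitivity analyses do not touch the issue: MCF and Clauss use the same ratio, and the 3-minute window in SAP 8.12 concerns timing. The rate before dichotomising carries more information about the treatment effect, yet it is only described. At stake is the precision of the evidence on fibrinogen correction, not the trial's primary conclusion.

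**Working it through.** **Inputs from the documents.** Method CV about 5% and cut 95% (Protocol 9.1.3.2); ratio of two readings (SAP 8.12); single baseline reading (SAP 8.2); 100 evaluable subjects per arm (Protocol 10.9).

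**Assumptions not in the documents.** The 5% is a per-reading CV; errors are normal and independent with the same CV at both times; the true restoring rates in each arm, which are varied below.

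**1. The plan's figure.** 100% − 1 × 5% = 95%. This reproduces the cut.

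**2. Error of the ratio.** 5% × √2 = 7.07%. The 5-point allowance is therefore 5/7.07 = 0.71 SD of the ratio; one SD would put the cut at 92.9%.

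**3. Misclassification at a true ratio r.** With error on both readings, P(fail) = Φ[(0.95 − r) / √((0.05r)² + (0.95 × 0.05)²)].
- r = 1.00: Φ(−0.05/0.0690) = 23.4%. With error on one reading only: Φ(−0.05/0.05) = 15.9%.
- r = 1.05: Φ(−0.10/0.0708) = 7.9%.
- r = 1.10: Φ(−0.15/0.0727) = 2.0%.
- r = 0.90: the subject passes with probability 1 − Φ(0.05/0.0654) = 22%.
- For per-reading CVs from 3% to 7%, the figure at r = 1.00 runs from 11% to 30%.

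**4. Effect on the arm difference.** Take true rates averaging 100% and 90%, with a between-subject SD of 10 points.
- Error-free classification at 95%: Φ(0.5) − Φ(−0.5) = 69.1 − 30.9, or 38 points.
- Error on one reading: about 35 points. Error on both: about 32 points. The second reading accounts for less than 3 of the 6 points lost.
- With an SD of 5 points, 68 becomes 45.
- Over a wider set (lognormal true ratios, medians 0.80 to 1.10, log-SD 0.10 to 0.20), the loss was about 0.2 to 8 points, of which the second reading contributed about 0 to 3.5.
- Dilution is not universal. With means of 110% and 100% and an SD of 5 points, error-free classification gives Φ(3) − Φ(1) = 99.9 − 84.1 = 16 points. With error, using the SDs of step 6 (0.0925 and 0.0866), it gives Φ(1.62) − Φ(0.58), or about 23 points.

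**5. Moving the cut to 93%.** In the 100% versus 90% example the observed difference goes from 32.2 to 32.0 points (SD 10) and from 45.0 to 44.2 (SD 5). Passes at a true 90% rise from 22% to 1 − Φ(0.03/0.0647) = 32%.

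**6. Continuous rate against dichotomy, 100 per arm.** The observed SD at mean m with between-subject SD s is about √(s² + (0.0707m)²).
- 100% versus 90%, s = 0.10: SDs 0.1225 and 0.1185, so z = 0.10 / √((0.1225² + 0.1185²)/100) = 5.9. The dichotomy gives 0.322/0.067 = 4.8 (4.6 with a pooled variance).
- 100% versus 96%, s = 0.10: SDs 0.1225 and 0.1209, so z = 0.04/0.0172 = 2.3. Simulated power is 64% for the continuous comparison and 46% for the dichotomy.
- The continuous z was the larger in every combination tried, with arm means between 80% and 110% and SDs from 5 to 20 points.

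**The case against.** The case against is substantial, and most of it stands.

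- **A quarter of restored subjects?** A reader might infer that about a quarter of all fully restored subjects are called failures. The documents do not support that. The 23% applies only at a true ratio of exactly 1.00. Averaged over subjects at or above baseline, it was about 3% to 13% in the assumed scenarios, and a single reading's error already accounts for 16 of the 23 points at exact baseline.
- **A generally diluted treatment effect?** This might also be inferred. It depends on where the arms lie. Against a target of true restoration to 100% or more, one scenario gave a true difference of 13.3 points and an observed 24.9; another gave 38.3 and 29.3.
- **A lower cut as the cure?** Step 5 shows that it trades false failures for false successes.
- **Whole-millimetre reading?** If A10 were reported in whole millimetres, 95% of any baseline from 9 to 19 mm would round up to the baseline itself. The documents do not state the reporting precision, and rounding also adds slack (24% failure at 10 mm, close to the unrounded 23%), so no conclusion rests on this.
- **Intent.** The Protocol states no target misclassification rate, and whether its CV refers to one reading rests on a cited source that is not part of the documents.
- **Impact.** The endpoint is exploratory, the trial is not powered on it, and the continuous rate is at least reported. In the 100% versus 90% example, power exceeds 99% either way. That dichotomising loses information is true of any responder endpoint.

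What remains is that the rationale does not describe the variable it is applied to, and that the more informative variable is derived but not compared.

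**Conclusion.** The mismatch holds. On the assumption of a 5% per-reading CV with independent errors, the ratio's CV is about 7%, and a subject exactly at baseline fails about 23% of the time instead of 16%, falling to 8% at a true 105% and 2% at 110%. The consequence for the arm difference cannot be fixed from the documents; in the scenarios tried it was often a few points, and in some it ran the other way. The case for change therefore rests on sensitivity rather than on bias: the continuous comparison outperformed the dichotomy in every scenario tried, and the gain matters mainly when the effect is modest (64% against 46% power in the 100% versus 96% example). This is a low-cost improvement to an exploratory secondary endpoint. It does not bear on the primary endpoint, the sample size or control of type I error.

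**What to change.** - **SAP 12.5.3.1:** keep the 95% CMH analysis. Add a between-arm comparison of the 15-minute FIBTEM A10 restoring rate as a continuous variable, using the ANOVA with predicted blood loss that SAP 12.5.3.3 and 12.5.3.4 already specify, and report the difference in least square means with its 95% CI.
- **Protocol 9.1.3.2 and SAP 7.2.1:** reword the rationale to say that the 5% is the error of one reading (once confirmed from the cited source) and that the ratio's error is then about 7%.
- **Protocol 9.1.2.2:** bring its definition, which omits the 95% tolerance, into line with 9.1.3.2 and SAP 8.12.

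The cost is some wording and one further table from a variable already derived. The downside is one more exploratory result on a secondary endpoint. No planned analysis is removed.
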